4.5.5. Definitions

The definition and details of the efficacy variables are listed as follows:

Total Nasal Symptom Score (TNSS)

The TNSS ranges from 0 to 12 and is based on assessment of 4 nasal symptoms graded on a Likert scale ranging from 0 (none) to 3 (severe) for nasal congestion, itching, and runny nose, and sneezing. The TNSS will be recorded before going to bed for the night using an e-diary.

Total Ocular Symptom Score (TOSS)

The TOSS ranges from 0 to 6 and is based on 2 eye symptoms: itching/redness/gritty feeling and tearing/watering. Each of the 2 symptoms is graded on a Likert scale ranging from 0 (none) to 3 (severe). The TOSS will be recorded before going to bed for the night using an e-diary.

Total Symptom Score (TSS)

The daily TSS is calculated by adding the TNSS and TOSS together, for a combined TSS of 0 to 18.

Daily Medication Score (DMS)

For the DMS, before going to bed for the night, patients will be asked to record their daily rescue medication use using an e-diary, including which medications and the amount of these pre-specified medications. This information will be used to calculate the DMS for the following medications or the approved in-class equivalents, as follows: desloratadine 5 mg 6 points/dose; maximum daily score 6 points, olopatadine 1 mg/mL each drop 1.5 points/drop; maximum daily score 6 points, mometasone furoate 50 ug/dose 2.0 points/spray; maximum daily score 8 points). The maximum DMS score is 20 (Calderon, 2014).

Combined Symptom and Medication Score (CSMS)

The daily CSMS is calculated by adding the DMS and TSS together, with scores ranging between 0 and 38. The method for calculating average CSMS is described in Section [5.6.1](#).

Skin Prick Test

An SPT with cat allergen extract, other relevant allergens, a negative control (such as saline/diluent), and a histamine positive control will be performed to assess sensitization status. A positive response for cat is defined by a mean wheal diameter (MWD) at least 5 mm greater than a negative control, in which SPT MWD is defined as $([\text{longest diameter} + \text{longest perpendicular}]/2)$. (Note: For other allergens, a positive sensitization is defined as a MWD of at least 3 mm greater than a negative control.)

The negative control mean wheal diameter will be subtracted from the SPT mean wheal diameter for presentation as a normalized MWD. In the case that the negative control MWD is larger than the allergen SPT MWD, the value of 0 mm will be used as the normalized MWD.

After week 12, the cat, house dust mite, and negative control SPT will be performed in replicate. Averages of the MWDs will be calculated for each allergen at the same visit and then the average of the two negative control MWDs will be subtracted to compute the normalized MWD.

Standardized Rhinoconjunctivitis Quality of Life Questionnaire [RQLQ(S)] for Ages 12+

The RQLQ(S) is a self-administered questionnaire to measure HRQoL in those 12 years of age and above, as a result of perennial or seasonal allergic rhinitis. There are 28 items on the RQLQ(S) in 7 domains: activity limitation, sleep problems, nasal symptoms, eye symptoms, non-nasal/eye symptoms, practical problems, and emotional function. The RQLQ(S) responses are based on a 7-point Likert scale with responses ranging from 0 (not troubled) to 6 (extremely troubled). The overall RQLQ(S) score is the mean of all 28 responses and the individual domain scores are the means of the items in those domains. Higher scores indicated more HRQoL impairment (lower scores were better). A change of 0.5 point or more in total score is considered to be clinically meaningful.

Asthma Nighttime Symptom Diary Score

Only for patients with asthma, upon waking up in the morning, patients will complete the e-diary to report asthma symptoms experienced during the nighttime using the Asthma Nighttime Symptom Diary (ANSO). The ANSD score will be based on 6 patient-reported symptoms (difficulty breathing, wheezing, shortness of breath, chest tightness, chest pain, and cough at their worst using an 11-point numeric rating scale (NRS) ranging from 0 ('None') to 10 ('As bad as you can imagine')).

Asthma Daytime Symptom Diary Score

Only for patients with asthma, before going to bed for the night, patients will complete the e-diary to report asthma symptoms experienced during the day using the Asthma Daytime Symptom Diary (ADSD). The ADSD score will be based on 6 patient-reported symptoms (difficulty breathing, wheezing, shortness of breath, chest tightness, chest pain, and cough at their worst using an 11-point numeric rating scale (NRS) ranging from 0 ('None') to 10 ('As bad as you can imagine')).

Asthma Daily Symptom Score

Only for patients with asthma, average of daily scores of the ANSD score and the ADSD score will be used to generate an Asthma Daily Symptom Score (ADSS) ranging from 0 ('None') to 10 ('As bad as you can imagine').

Juniper Asthma Control Questionnaire

Only for patients with asthma, the ACQ-5, (5-question version of the Juniper ACQ), is a validated questionnaire to evaluate asthma control. The ACQ-5 score is the mean of the scores of the 5 items and ranges from 0 (totally controlled) to 6 (severely uncontrolled). Scores less than 1.0 reflect adequately controlled asthma, and scores 1.0 or greater reflect inadequately controlled asthma. Higher score indicates lower asthma control and 0.5 is the smallest change that can be considered clinically important.

FEV1

Before randomization, in-clinic spirometry will be performed on all patients to determine FEV1 (forced expiratory volume in 1 second) in liters (L). After randomization, in-clinic spirometry will only be performed for patients with asthma.

4.6. Safety Variables

4.6.1. Adverse Events and Serious Adverse Events

Adverse events and serious adverse events will be collected from the time of informed consent signature and then at each visit until the end of the study. All adverse events are to be coded to a “Preferred Term (PT)” and associated primary “System Organ Class (SOC)” according to the Medical Dictionary for Regulatory Activities (MedDRA).

An Adverse Event is any untoward medical occurrence in a patient administered a study drug which may or may not have a causal relationship with the study drug. Laboratory results, vital signs, or ECG abnormalities are to be recorded as AEs if they are medically relevant: symptomatic, requiring corrective therapy, leading to treatment discontinuation and/or fulfilling a seriousness criterion.

For safety variables, 4 observation periods are defined:

- The pretreatment period is defined as the time from signing the ICF to before the first dose of study drug.
- The on-treatment period is defined as the day from first dose of study drug to the last dose of study drug plus 12 weeks (visit 3 to visit 14).
- The follow-up period is defined as the end of the on-treatment period to 12 weeks after the end of the on-treatment period (visit 14 to visit 15).
- The overall study period is defined as the day from first dose of study drug to the end of study visit (on-treatment period plus follow-up period)

Treatment-emergent adverse events (TEAEs) are defined as those that are not present at baseline or represent the exacerbation of a pre-existing condition during the on-treatment and follow-up periods.

A Serious Adverse Event is an adverse event (AE) that is classified as serious according to the criteria specified in the study protocol 10.2.2.

4.6.2. Adverse Events of Special Interest

An adverse event of special interest (AESI; serious or non-serious) is one of scientific and medical interest specific to the sponsor’s product or program, for which ongoing monitoring and rapid communication by the investigator to the sponsor can be appropriate. Such an event might warrant further investigation in order to characterize and understand it. List of AESI and AESI criteria is specified in Section 10.4.

Adverse events of special interest for this study include:

- Severe or systemic hypersensitivity reactions (including anaphylaxis) defined using the narrow SMQ for hypersensitivity, with blinded manual adjudication of relevant PTs by medical monitor before database lock.
 - For SMQ “anaphylactic reaction”, an algorithmic approach will be used. Details are provided in Section 10.4.
- Asthma exacerbations defined using the narrow SMQ for asthma and further manual blinded adjudication before database lock for events requiring treatment with systemic corticosteroids or resulting in an emergency room visit or hospitalization.

4.6.3. **Laboratory Safety Variables**

Hematology, chemistry, urinalysis, and pregnancy testing samples will be analyzed. Detailed instructions for blood sample collection are in the laboratory manual provided to study sites.

Samples for laboratory testing will be collected. Tests will include:

Blood chemistry

Sodium	Total protein, serum	Aspartate aminotransferase (AST)
Potassium	Creatinine	Alanine aminotransferase (ALT)
Chloride	Blood urea nitrogen (BUN)	Alkaline phosphatase
Carbon dioxide	Total bilirubin	Albumin
Calcium	Glucose	

Hematology

Hemoglobin	Differential:
Hematocrit	Neutrophils
Red blood cells (RBCs)	Lymphocytes
White blood cells (WBCs)	Monocytes
Red cell indices	Basophils
Platelet count	Eosinophils

Urinalysis

Color	Glucose	RBC
Clarity	Blood	WBC
pH	Bilirubin	Bacteria
Specific gravity	Leukocyte esterase	Epithelial cells
Ketones	Nitrite	Yeast
Protein		

Other laboratory tests

4.6.4. Vital Signs

Vital signs include systolic and diastolic blood pressure, respiratory rate, and heart rate. Vital signs will be collected in a seated position. On the day of study drug administration, vital signs are taken prior to PK blood draw, prior to study drug administration, and at 2 hours (± 10 min) after completion of the injection.

Weight and height are measured at screening visit 1 only.

4.6.5. Physical Examination Variables

A thorough and complete physical examination will be performed. Care should be taken to examine and assess any abnormalities that may be present, as indicated by the patient's medical history.

4.6.6. Spirometry

Spirometry measurements include FVC (L), FEV1 (L), FEV1/FVC, PEF (L/s), FEF 25-75 (L/s). Spirometry (American Thoracic Society [ATS]/European Respiratory Society [ERS]-compliant) (Graham, 2019), as adjudicated during the centralized OverRead review, will be performed locally during the study at specified time points. Spirometry details will be available in a separate operational manual provided to the sites. Additional data handling conventions are presented in Section 6.3.

4.7. Pharmacokinetic Variables

Concentrations in serum of total (free+antigen bound) REGN1908 and REGN1909 will be determined at time points specified in the study schedule of events in Appendix Section 10.2. Pharmacokinetic variables consist concentrations individual drug (REGN1908 and REGN1909), and total drug (REGN1908+REGN1909) in serum, and time (both nominal and actual time).

4.8. Immunogenicity Variables

The immunogenicity variables include ADA status, titer and NAb status at nominal sampling time/visit. Serum samples for ADA will be collected at the clinic visits specified in Appendix 10.2. Samples positive in the REGN1908-1909 ADA assay will be further characterized for ADA titers. Anti-REGN1908, and anti-REGN1909 neutralizing antibodies (NAb) analysis may be performed on ADA-positive serum samples. The overall immunogenicity risk will be taken into consideration to assess the need for NAb analysis. Serum samples will be banked, if NAb analysis is to be conducted at a later time.

4.9. Biomarker Variables

Exploratory biomarker variables include:

- Serum for specific IgE for Fel d 1
- Serum for specific IgE for cat dander
- Serum for sIgE for Fel d 2, 4, and 7 at baseline, week 12 (V6), week 60 (V14)
- Serum for sIgE for other allergens (e.g., HDM, etc.)

5. STATISTICAL METHODS

For continuous variables, descriptive statistics will include the following: the number of patients reflected in the calculation (n), mean, median, standard deviation, minimum, and maximum.

For categorical or ordinal data, frequencies and percentages will be displayed for each category. Missing values at baseline will not be imputed unless otherwise specified.

5.1. Demographics and Baseline Characteristics

Demographics and Baseline Characteristics will be summarized by treatment groups and overall based on the FAS.

5.2. Medical History

Medical history will be summarized by primary SOC and PT for each treatment group and for study total based on the SAF. The table will be sorted by decreasing frequency of SOC followed by PT based on the overall incidence across treatment groups. Number/proportion of each medical history, listing all the values in allergy form.

5.3. Prior/Concomitant Medications/Procedures

The number and proportion of subjects taking prior medications will be summarized, as well as the number and proportion taking concomitant medications during the treatment and follow-up periods (separately) based on the FAS. Similar tables will be provided for the number and proportion of subjects taking prohibited medications. Prohibited medications taken in the first and last 12 weeks of the treatment period may also be presented separately. Each table will be sorted by decreasing frequency of Anatomical Therapeutic Chemical (ATC) level 2 and ATC level 4 based on the overall incidence. Subjects will be counted only once for each medication class (ATC levels 2 and 4) linked to the medication.

Number of patients taking rescue medications will be summarized by medication name based on rescue medication e-diary based on the FAS. The frequency of rescue medication use during the efficacy assessment periods may also be summarized.

Number and proportion of patients taking prior/concomitant procedures will be summarized for study total based on the SAF, sorted by decreasing frequency of SOC and PT based on the overall incidence. Patients will be counted only once for each SOC and PT linked to the procedure. Number of patients receiving prior immunotherapy (SLIT, SCIT) will be summarized separately.

5.4. Subject Disposition

The following summaries will be provided for each treatment group and total (unless otherwise specified):

- The total number of screened subjects who signed ICF, along with reasons for screen failure (for study total only)
- The total number of randomized patients: received a randomization number from IWRS
- The total number of patients in each analysis set
- The total number of randomized patients who discontinued the study and the reasons for discontinuation (including COVID-19 related reasons)
- The total number of randomized patients who completed the study treatment and discontinued the study treatment with the reason of discontinuation (including COVID-19 related reasons)

5.5. Extent of Study Treatment Exposure

5.5.1. Exposure to Investigational Product

The duration of exposure during the study will be calculated as follows:

$$(\text{date of last dose of study drug} - \text{date of first dose of study drug}) + 84 \text{ days}$$

The calculations do not take into account temporary dosing interruption including due to COVID-19. The summary of exposure to study drug will include the number of study drug doses and injections administered and the duration of exposure. Duration of exposure will be summarized for each treatment group using the number of patients, mean, SD, minimum, median, Q1, Q3, and maximum.

In addition, the duration of exposure will be summarized categorically by counts and percentages for each of the following categories cumulatively by these categories: ≥ 85 days (> 12 weeks), ≥ 169 days (> 24 weeks), ≥ 253 days (> 36 weeks), ≥ 337 days (> 48 weeks), and ≥ 365 days (> 52 weeks).

The duration of observation period during the study in days is calculated as:

$$(\text{Date of the last visit} - \text{date of the first study drug injection}) + 1.$$

The duration of observation period will be summarized descriptively using number of patients, mean, SD, median, Q1, Q3, minimum and maximum. In addition, the number (%) of subjects with observation periods will be presented by specific time periods. The time periods of interest are specified as:

< 85 days, ≥ 85 days, ≥ 169 days, ≥ 253 days, ≥ 337 days, ≥ 421 days, and ≥ 505 days.

5.6. Analyses of Efficacy Variables

5.6.1. Analysis of Primary Efficacy Variable

The analyses of efficacy variables are described in the subsections below and summarized in Section 10.1.1 of the Appendix. The intercurrent events, strategies, and the corresponding missing data handling approaches for the primary estimands of interest for the primary endpoint are provided in Table 4.

Table 4: Summary of Estimand for Primary Endpoint

Endpoint Category	Estimand			
	Endpoint(s)	Population	Intercurrent event(s) handling strategy and missing data handling	Population-level summary
Primary endpoint	Daily combined symptom and medication scores (CSMS) averaged over the last 12 weeks of the treatment period	FAS	
The intercurrent events will be handled as follows¹:
 
 1. Discontinuing the study intervention: all data collected after discontinuation will be used in the analysis (treatment policy strategy) 2. Rescue treatment and select prohibited medications^{2,3} taken to treat allergic symptoms during the last 12 weeks of the efficacy assessment period: data after medication will be used in the analysis (treatment policy strategy) 3. Prohibited medications taken during the efficacy assessment period which are adjudicated to be handled using a composite strategy³: 
 a. The daily CSMS, starting from the day the prohibited medication was taken through the end of the last 12 weeks of efficacy assessment, will be imputed by worst CSMS score (largest observed TNSS+TOSS+DMS) observed before prohibited medications were taken from the same patient. The average CSMS will be calculated using observed components prior to receiving prohibited medication and imputed values after prohibited medication. b. If no values of CSMS⁴ are available during the last 12 weeks of the efficacy assessment period prior to the patient taking prohibited medication, the daily CSMS will be imputed using the worst average CSMS score during the last 12 weeks of all observations in the corresponding treatment group 4. Prohibited medications taken during the efficacy assessment period which are adjudicated to be handled using a hypothetical strategy³: data during use of medication and during washout period will be set to missing 5. Change in cat allergen exposure: 
 a. If no cat is living in the patient's home during all or part of the last 12 weeks of the treatment period: all available data will be used in analysis (treatment policy) b. If patient travels away from home for less than 42 consecutive days: all available data will be used in 	
ANCOVA model with treatment group, stratification factors, and cat sIgE (<17.5 kUa/L versus \geq17.5 kUa/L) as fixed factors and baseline CSMS as a covariate.
 
The least squares means (LS-means) estimates for the average CSMS during the last 12 weeks of the treatment period for each treatment group, as well as the difference between the REGN1908-1909 and placebo will be provided along with the corresponding 2-sided p-value and associated 95% confidence interval.


Endpoint Category	Estimand			
	Endpoint(s)	Population	Intercurrent event(s) handling strategy and missing data handling	Population-level summary
			
analysis (treatment policy); otherwise, for travel \geq 42 consecutive days, a hypothetical strategy will be used where data during patient travel will be set to missing
 
In addition, the missing data imputation rules for patients who have no available values of CSMS⁴ during the last 12 weeks of the treatment period are as follows:
 
 Missing data due to patients' discontinuation from study due to AEs and lack of efficacy will be imputed using worst average CSMS score during the last 12 weeks of all observations in the corresponding treatment group Missing data due to any other reason will be imputed using MI 	

[1] If a data point or missing value falls into multiple categories of intercurrent events as specified above, the following priority order for handling of data will be applied: ICE 3), ICE 4), ICE 5b) ICE 5a), ICE 1), ICE 2). For example, if data or missing value fall into both ICE 3) and 5a), the strategy for ICE 3) should be followed, as it takes priority over 5a).
 
[2] Select prohibited medications that will be handled using a treatment policy are listed in Category 1 of Table 7
 
[3] Additional prohibited medications listed in Category 2 Table 7 will undergo blinded adjudicated by study medical monitor before the database lock to determine if they will be handled by treatment policy, composite strategy, or hypothetical strategy
 
[4] No available values of CSMS means no available TNSS, TOSS, or DMS during the last 12 weeks of the efficacy assessment period
				

The primary analysis will focus on the comparison between REGN1908-1909 and placebo in the FAS. The analysis will be performed using an analysis of covariance (ANCOVA) model, with the treatment group, randomization stratification factors (as stratified), and cat sIgE (<17.5 kUa/L versus ≥ 17.5 kUa/L) as fixed effects and the baseline CSMS as a covariate. The baseline CSMS will be calculated as the average CSMS during the first 15 consecutive days of the baseline assessment period where eligibility criteria (for TSS and rescue medication use) were met, as specified based on the following two criteria:

1. Must have at least 8 unique days of a TSS score ≥ 8 within a 15 consecutive day period.
2. Must have a least 8 unique days of a DMS score >0 within the same 15 consecutive day period as Criteria 1. The 8 unique days do not have to occur on the same days as Criteria 1; however, they must be within the same 15 consecutive days.

If less than 15 days of data are available during the baseline assessment period, the baseline will be the average CSMS over all available days (if duplicate entries of CSMS are available on the same day, the worst score will be used).

Only days with observed data will be included in the calculation of average score. The average CSMS (max score 38/day) will be calculated based on the sum of average daily TNSS (max score 12/day), average daily TOSS (max score 6/day) and average daily medication scores (DMS, max of 20/day) recorded over the last 12 weeks of the treatment period (weeks 48 to 60).

For the MI procedure, missing data (the average CSMS) will be imputed 50 times to generate 50 complete data sets utilizing the SAS procedure PROC MI. Note that any imputation by worst CSMS score as specified in [Table 4](#) will occur prior to MI. The 2 steps below will be followed for MI:

Step 1: The Markov Chain Monte Carlo (MCMC) method will be used to fill in missing values of average CSMS during weeks 0-12 by treatment group so that a monotone missing pattern will be formed.

Step 2: Using the data sets from Step 1, missing values of average CSMS from weeks 48-60 will be imputed using a monotone regression method. The imputation model will include the covariates in the ANCOVA model and the average CSMS from weeks 0-12.

For steps 1 and 2, any score imputed outside the range of CSMS (0-38) will be truncated to the nearest value of CSMS according to the following algorithm:

- If the imputed score > 38, then the final imputed score will be 38.
- If the imputed score < 0, then the final imputed score will be 0.

Sample SAS syntax code for MI:

```
proc mi data=mi1 out=mi3 noint nimate=50 seed=190819;
mcmc impute=monotone;
var BASELINE CSMS012 CSMS4860;
by TRTP;
run;

proc mi data=mi3 out=mi4 nimate=1 seed=190819;
class TRTP STRAT1 STRAT2 STRAT3 CATIGE;
monotone reg;
var TRTP STRAT1 STRAT2 STRAT3 CATIGE BASELINE CSMS012;
by _imputation_;
run;
```

Each imputed data set will then be analyzed by ANCOVA as previously described. The SAS procedure PROC MIANALYZE will be used to generate valid statistical inferences by combining results from these 50 ANCOVA analyses using Rubin's formula. The least squares means (LS-means) estimates for the average CSMS during the last 12 weeks of the treatment period for each treatment group, as well as the difference between the REGN1908-1909 and placebo will be provided along with the corresponding 2-sided p-value and associated 95% confidence interval.

Sensitivity analysis:

With respect to the missing data handling of daily entries, sensitivity analyses will be performed to confirm robustness of the conclusion drawn based on the main model for primary analysis.

Tipping Point Analysis

Sensitivity analysis using a tipping point approach with MI will be performed to assess the robustness of the results due to data that may be missing not-at-random (MNAR). The impact from missing data on comparisons of average CSMS during the last 12 weeks between REGN1908-1909 and placebo will be examined.

This approach will introduce a sensitivity parameter, δ . Estimations will be performed using MI methodology. Missing data will be imputed 50 times to generate 50 complete data sets utilizing the SAS procedure PROC MI for each δ following the 2 steps as previously described, where δ will be added to each of the imputed values (of average of last 12 weeks) for patients in the REGN1908-1909 arm. (Note that when $\delta=0$, this aligns with the standard MI analysis assuming missing at random (MAR).) Scores that are adjusted to outside the range of CSMS will be truncated in the same manner as previously described for the MI method.

Each imputed data set will then be analyzed by ANCOVA as previously described. For each δ , the SAS procedure PROC MIANALYZE will be used to generate valid statistical inferences by combining results from these 50 ANCOVA analyses using Rubin's formula. By progressively increasing δ , the sensitivity analysis will explore the “tipping point”, where the result is no longer statistically significant (i.e., $p\text{-value}>0.049$).

Additional Sensitivity Analyses

An additional sensitivity analysis may be performed when determining asthma status from medical history and house dust mite sensitization status from lab data, rather than as stratified.

Supplemental Analyses

Additional sensitivity analysis will also be performed for the handling of data after relevant prohibited medications. After use of prohibited medication, daily CSMS will be imputed by the worst score in the corresponding treatment group, and with the worst 5th percentile score in the corresponding treatment group, as a way to consider a reasonable range of “poor” scores to impute the missing data.

A supplemental analysis will also be performed where all intercurrent events are handled via a treatment policy, regardless of type of prohibited medication taken or change in cat exposure.

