10.5. Prohibited Medications Relevant for Analysis

Prohibited medications as defined in Section 4.4 have been further categorized into groups based on their expected impact on the efficacy variables and planned data handling method:

- **Category 1** – Medications that are not expected to impact efficacy variables (treatment policy)
- **Category 2** – Medications that require blinded adjudication (considering factors such as the type of medication, indication, timing, and frequency) to determine if data should be handled by treatment policy, composite strategy (in the case of medications that are expected to impact efficacy variables and may be indicative of treatment failure), or hypothetical strategy (in the case of medications that are expected to impact efficacy variables but are not indicative of treatment failure)
- **Category 3** – Medications that are expected to impact efficacy variables, but are not indicative of treatment failure (hypothetical strategy)

These categories have been defined separately for the following groups of endpoints:

- CSMS, TNSS, TOSS, DMS and RQLQ(S)+12 endpoints ([Table 7](#))
- Asthma-related endpoints ([Table 8](#))
- SPT endpoints ([Table 9](#))

Table 7: Prohibited medication categories for CSMS, TNSS, TOSS, DMS and RQLQ(S)+12 endpoints

Category 1	Category 2
Treatment policy	Adjudication to determine treatment policy, composite strategy, or hypothetical strategy
1st gen, 2nd gen oral antihistamines/ intranasal antihistamines/ ocular antihistamines	Corticosteroids (intra-muscular/ intra-articular/ extended duration implants such as intravitreal etc)
Longer acting antihistamines (eg, Hydroxyzine/ Cyproheptadine)	Oral/ IV corticosteroids
Topical/ oral decongestants	Systemic calcineurin inhibitors
Intranasal anticholinergics	
SIT with any allergen other than cat
 
Immune directed biologics and/or therapies that would interfere with Type 2 allergic disease or suppress the immune system, including but not limited to anti-IgE, anti IL-5, anti IL-4
 
Specific immunotherapy (SIT) with cat allergen or vaccines against cat allergy

Intranasal corticosteroids	
Ocular corticosteroids	
Ocular/intranasal cromoglycates	
Methylxanthines	
Leukotriene modifiers	

Table 8: Prohibited medication categories for asthma-related endpoints

Category 1 Treatment policy	Category 2 Adjudication to determine Treatment Policy, Composite Strategy, or Hypothetical Strategy	Category 3 Hypothetical Strategy (Multiple Imputation)

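### SAP Table 4, event 3a has no floor at the recorded score and no stated look-back, so a possible treatment failure early in the window, or with lasting worsening, can score better than the patient's own diary

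*SAP*

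**What the plan says.** Event 3 in SAP Section 5.6.1, Table 4 covers prohibited medications that blinded adjudication assigns to the composite strategy. Section 10.5 describes that route as "composite strategy (in the case of medications that are expected to impact efficacy variables and may be indicative of treatment failure".

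- **3a, days replaced:** "The daily CSMS, starting from the day the prohibited medication was taken through the end of the last 12 weeks of efficacy assessment".
- **3a, replacement value:** each of those days "will be imputed by worst CSMS score (largest observed TNSS+TOSS+DMS) observed before prohibited medications were taken from the same patient".
- **3a, average:** "The average CSMS will be calculated using observed components prior to receiving prohibited medication and imputed values after prohibited medication".
- **3b:** this part covers a patient with no CSMS entry inside the last 12 weeks before first use. That patient's score "will be imputed using the worst average CSMS score during the last 12 weeks of all observations in the corresponding treatment group".

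Table 4 footnote 1 puts event 3 ahead of every other intercurrent event. Section 5.6.2 carries the Table 4 strategy over to TNSS, TOSS, TSS and DMS in both 12-week windows, and Section 7.2 uses the Section 5.6 methods at the futility analysis. Under the supplemental analyses, Section 5.6.1 adds imputation with the arm's worst score, imputation "with the worst 5th percentile score in the corresponding treatment group", and an analysis that treats all intercurrent events by treatment policy.

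**The concern.** Three things are missing from 3a.

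1. **A floor.** The recorded scores on the day of use and afterwards are replaced without being compared with the replacement. Symptoms and rescue use are entered at bedtime, so the day-of-use entry can hold the flare that led to the medication. If that entry or a later one is the patient's worst, the rule substitutes something milder.
2. **A look-back period.** 3a does not say how far back the search for the worst score runs. The trigger for 3b refers to the last 12 weeks, which implies an in-window search, but 3a does not say so. The summary in SAP Section 1.2.4 mentions only the patient's worst score.
3. **A minimum number of prior days.** If the search is in-window, a patient with one earlier diary day gets that day's score for the rest of the window, while a patient with none gets the worst average in the arm.

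A composite strategy is meant to count the event as an unfavourable outcome, and a replacement below the patient's own record does the opposite. The rule reaches the primary endpoint and ten of the twelve ranked secondary endpoints in Section 5.6.3 (ranks 2, 4 to 9 and 11 to 13).

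**Working it through.** **Inputs from the documents.** Placebo mean CSMS 9.1, between-patient SD 6.2 and planned difference 1.8 (SAP Section 2.3); window of 84 days (Section 6.5); CSMS range 0 to 38 (Section 4.5.5). The plan gives no figure for this rule. Its sample size reproduces from these inputs: 2 × (1.9685 + 1.2816)² × (6.2/1.8)² = 250.6, or 251 per arm at two-sided 0.049.

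**Assumptions.** The documents give neither the within-patient daily SD nor the share of patients affected. I take a daily SD of 4 (3 to 5 in step 4), a day-to-day correlation of 0 to 0.8, and an in-window look-back unless stated.

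**Step 1: size of the replacement.** With *k* independent prior days, the expected worst score is the patient's mean plus SD × E(k), where E(k) is the expected maximum of *k* standard normals.

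| Prior days | E(k) | 9.1 + 4 × E(k) |
|---|---|---|
| 1 | 0 | 9.1 |
| 3 | 0.85 | 12.5 |
| 7 | 1.35 | 14.5 |
| 14 | 1.70 | 15.9 |
| 42 | 2.18 | 17.8 |

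**Step 2: single days.** With no worsening and independent days, a given later entry exceeds the replacement with probability 1/(k+1): 50%, 25% and 12.5% after 1, 3 and 7 prior days. With a 4-point flare at use, that day's entry exceeds it in 76 to 94%, 55 to 78% and 39 to 60% of patients (correlation 0 to 0.8).

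**Step 3: the 12-week average, which is the endpoint.** Simulated for a patient with mean 9.1 and daily SD 4. Percentages are patients whose 3a average is better (lower) than their diary average, over correlations 0 to 0.8. Means are at correlation 0.5.

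| Prior days | No worsening: better | Diary / 3a mean | Persistent +4: better | Diary / 3a mean |
|---|---|---|---|---|
| 1 | 50% | 9.1 / 9.1 | 84% | 13.1 / 9.1 |
| 3 | 13–33% | 9.1 / 11.6 | 60–73% | 13.0 / 11.6 |
| 7 | 1–17% | 9.1 / 13.3 | 30–58% | 12.8 / 13.4 |
| 14 | 0–7% | 9.1 / 14.3 | 10–40% | 12.4 / 14.3 |

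Hand check of the first row with persistent worsening: the diary averages (1 × 9.1 + 83 × 13.1)/84 = 13.05, and 3a gives 9.1 throughout.

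**Step 4: use spread evenly over the window.** Patient means 9.1 (SD 6.2), daily SD 3 to 5, correlation 0 to 0.8, scores limited to 0–38.

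- No worsening: the 3a average is better than the diary in about 2 to 5% of affected patients, and on average 2 to 4 points worse.
- Persistent +4: better in about 5 to 36%.
- Persistent +4 with use in the first week (1 to 7 prior days): better in about 45 to 80%. Those days are 7 of the 83 days that have at least one prior day, or 8%.

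**Step 5: the look-back matters.** If baseline and weeks 0–12 also count (15 + 84 = 99 days), the worst score lies about 2.5 SDs above the mean, 9.1 + 4 × 2.5 = 19.1, even on the second day of the window. Baseline alone sets a minimum. A patient who meets both criteria in Section 5.6.1 has at least 8 days with TSS of 8 or more and at least 8 days with DMS above 0 in the same 15 days. These overlap on at least 8 + 8 − 15 = 1 day. With the smallest medication score of 1.5, that day's CSMS is at least 9.5.

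**Step 6: effect on an arm mean.** Take the unfavourable case in which every affected patient has one prior day and a persistent +4. The understatement is 13.06 − 9.14 = 3.92 points per patient. If 1 to 5% of an arm were affected, its mean would move by 0.04 to 0.20, against a planned difference of 1.8.

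**The case against.** Leaving out scores from the day of use is deliberate. Protocol Section 11.4.3.1 sets CSMS to missing from that point because the medication may alter symptoms, and a bedtime entry may already reflect it. That is a good reason not to use a lower score recorded after the medication. It is no reason to discard a higher one, so the missing floor stands.

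The scope is narrow. Antihistamines, decongestants, intranasal corticosteroids and leukotriene modifiers are Category 1 in SAP Table 7 and follow treatment policy. Only Category 2 medications adjudicated as composite reach 3a, and that category includes immunotherapy and intra-articular steroids, which need not follow a flare. This limits the size of the problem and stands.

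The supplemental analyses would expose much of the effect, and SAP Section 1.2.5 says the strategy was updated on regulatory feedback. Both are true. But none of those analyses takes the larger of recorded and imputed scores, and the primary estimand keeps the rule as written.

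A reader might infer that 3a usually favours failures. Step 4 shows the opposite for the 12-week average. A reader might also infer that an early failure is scored as an average patient. That needs the in-window look-back, which 3a does not state, and even then fits only about the first 1 to 3 prior days.

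**Conclusion.** The point holds in a limited form. As written, 3a can score a possible treatment failure better than the patient's own record. This is uncommon across the window as a whole. It becomes likely when use falls in roughly the first week and symptoms then stay worse, and it occurs in a sizeable minority of early events even without worsening. The step from the arm's worst average (no prior window day) to a single day's score (one prior window day) exists only under the in-window reading.

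It would be tempting to say that the rule dilutes the treatment difference. The documents do not support that: they give no event rates by arm, and because 3a usually raises the average above the diary, more events on placebo could equally widen the difference. The number of affected patients is also unknown. The percentages depend on the assumed daily SD, correlation and pattern of worsening. The missing floor and look-back follow from the text alone. This is a clarification worth making before database lock, and nothing here shows that the primary conclusion is at risk.

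**What to change.** Reword 3a along these lines: *each day from first use of the medication to the end of the assessment window is assigned the larger of (i) the patient's worst daily CSMS over the baseline assessment period and the current assessment window, up to and including the day of first use, and (ii) the CSMS recorded on the day being imputed, if there is one.* The current window is weeks 0–12 or weeks 48–60, according to the endpoint. Apply the same rule to TNSS, TOSS, TSS and DMS, each on its own scores, and note that separately imputed components need not add up to the imputed CSMS. State also whether 3b still applies to a patient who has baseline days but no window day before use; if it does, the step to the arm's worst average remains for that patient.

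This keeps the composite strategy and never lets a score lowered by the medication replace a worse one. The cost is SAP wording and one extra derivation step. The average becomes slightly less favourable for the few affected patients in either arm. If the present wording was agreed with a regulator, the change should be shown to it.
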